1. BACKGROUND

1.1 BACKGROUND ON COPD

Chronic obstructive pulmonary disease (COPD) has been defined as a clinical syndrome characterized by chronic respiratory symptoms, structural pulmonary abnormalities (airways disease and/or emphysema), and lung function impairment (primarily airflow limitation that is poorly reversible). The characteristic symptoms of COPD are dyspnea, cough, and sputum production (Global Initiative for Chronic Obstructive Lung Disease [GOLD 2019]). The GOLD staging system expresses COPD severity, as reflected by symptoms, history of worsening, requirements for hospital stay, and spirometric measures of lung function and includes stages: GOLD 1 (mild), GOLD 2 (moderate), GOLD 3 (severe), and GOLD 4 (very severe).

COPD is a significant cause of morbidity and mortality worldwide (GOLD 2019). In contrast to other chronic diseases, COPD is increasing in prevalence and is projected to be the third-leading cause of death and disability worldwide by 2030 (GOLD 2019). Worldwide estimation of the overall prevalence of Stage ≥ 2 (moderate) COPD is 10.1% (Buist et al. 2007). COPD is caused by long-term exposure to inhaled noxious gases and particles. Cigarette smoke accounts for more than 90% of cases in developed countries. COPD usually occurs in patients over the age of 40 years and is more common in men.

The costs to society for treating COPD are high, accounting for approximately 3.4% of the total health care budget of the European Union. In the United States, medical costs for treatment of COPD were \$32.1 billion in 2010 and are estimated to increase to \$49 billion by 2020 (Ford et al. 2015). Acute exacerbations of COPD (AECOPD) are responsible for a large portion of the economic burden, morbidity, and mortality of the disease and are attributed to more than 500,000 hospitalizations and 100,000 deaths in the United States each year.

COPD is a heterogeneous disease, and there are currently no clear methods to identify patients with a high risk of acute exacerbations (AEx), particularly in mild COPD. For example, although patients with a history of exacerbations and/or reduced forced expiratory volume (FEV₁) are considered at higher risk for future adverse outcomes and subsequent disease progression (Donaldson and Wedzicha. 2006; Agusti et al. 2010; GOLD 2019), patients with mild disease also have AEx (Han et al. 2017). To date, the strongest predictor of exacerbation risk is a prior history of exacerbation.

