4.2 METHOD OF TREATMENT ASSIGNMENT AND BLINDING

Patients will be randomized to the treatment arms through the interactive voice/web-based response system (IxRS). After written informed consent has been obtained, patients in Cohort A will be randomized in a 1:1 ratio to one of two open-label treatment arms (azithromycin, 250 mg/QD plus daily SOC medications or daily SOC medications). Patients in Cohort B will continue to receive daily SOC medications.

Permuted block randomization will be performed centrally for Cohort A and stratified by region (United States or United Kingdom/Canada) and prior exacerbation history (2, ≥ 3). During the open-label treatment period, the IxRS will make study treatment kit assignments.

In Cohort A, the number of COPD patients with chronic bronchitis (COPD-CB) will be capped at ≤ 65 .

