6. STATISTICAL CONSIDERATIONS AND ANALYSIS PLAN

6.1 DETERMINATION OF SAMPLE SIZE

Power calculations for this exploratory study require many assumptions due to lack of available literature on the ¹²⁹Xe MRI metrics. Further details than those provided in the protocol, including code to generate these calculations, are available in the Statistical Analysis Plan (SAP). All calculations were done in R version 3.5.0. The focus of this trial is on estimation, not hypothesis testing.

The main objective of this study is establishing if ^{129}Xe MRI metrics (VDP) are a more sensitive measure of lung function decline and can predict the rate of moderate/severe exacerbation. Approximately 100 patients in Cohort A will be enrolled in this study. A sample size of 100 will enable enough exacerbations to anchor the evaluation of the performance of VDP.

This study is powered (at 77%) to detect a treatment effect due to exacerbation, depending on assumptions. Power calculation was done based on a negative binomial with over-dispersion of 1.3 (COPD BEAT data), with 5% alpha, assuming a mean exacerbation frequency of 2 and observed for 48 weeks. A one-sided test was used and 10% drop-out rate. A further assumption on the azithromycin effect size was needed to establish power—a 35 % reduction rate ratio was used (Seemungal et al. 2008).

This study is powered, depending on assumptions, for the secondary efficacy objectives. To test the sensitivity of VDP metric relative to FEV_1 (coefficient of variation test), a sample size of 100 provides just under 90% power to establish improved coefficient of variation relative to FEV_1 (assumes coefficient of variation observed in Weatherly et al. 2019 of 180% and using a simulation-based power calculation run with MSLR and a p-value of 0.05.)

This study is well powered to test the secondary efficacy objective of establishing the relationship between HRCT metrics and the VDP metric. With a sample size of 100, and assuming a true correlation of 0.25 between the metrics, the study has approximately 75% power to determine if a correlation exists (assuming a multivariate normal with correlation of 0.25 and PRM^{SAD} mean of 26.6% and standard deviation of 11.6% [Bhatt et al. 2016]). Assumptions of operating characteristics of ^{129}Xe MRI metric, VDP, come from Smith et al. 2018 (mean=4.37, SD=1.89).

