6.4 EFFICACY ANALYSES

The analysis population for the efficacy analyses will consist of all patients, with patients grouped according to their assigned treatment.

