6.4.1 Primary Efficacy Endpoints

The primary efficacy endpoints are detailed in Section [2.1.1](#).

Details of the analysis are available in the SAP, including sensitivity analysis. At a minimum, VDP change at 24 weeks can predict rate of moderate/severe COPD exacerbation over 48 weeks, controlling for treatment assignment. The initial model will be a negative binomial model for exacerbation rate using the intent-to-treat (ITT) population. As this is an exploratory study, sensitivity analysis is performed for the purpose of confirming signal. If signal is not found using the primary analysis, sensitivity analysis will not be performed.

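### Section 6.4.1 does not commit the primary negative binomial model to the two randomization factors, including the exacerbation history that the protocol calls the strongest predictor of the outcome

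*Combined protocol and SAP*

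**What the plan says.** **Primary model.** Protocol Section 6.4.1, repeated in the synopsis, states: "The initial model will be a negative binomial model for exacerbation rate using the intent-to-treat (ITT) population". The predictor of interest is VDP change from baseline to Week 24, which "can predict rate of moderate/severe COPD exacerbation over 48 weeks, controlling for treatment assignment". The sentence opens by calling this a minimum. The same section says "Details of the analysis are available in the SAP, including sensitivity analysis". It adds that no sensitivity analysis will be done if the primary analysis shows no signal.

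**Randomization.** Under Section 4.2, Cohort A is "stratified by region (United States or United Kingdom/Canada) and prior exacerbation history" (2 versus 3 or more events). Section 3.1 counts those events over the prior 12 months.

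**Prognostic importance.** Section 1.1 states: "To date, the strongest predictor of exacerbation risk is a prior history of exacerbation".

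**Population.** Section 6.4 states: "The analysis population for the efficacy analyses will consist of all patients". Read literally, this includes Cohort B, which is observational and not randomized.

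Nothing in Section 6 places region or exacerbation history in a model, and nothing excludes them. No SAP text was available for this review.

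**The concern.** Randomization balances exacerbation history between the two arms, so for a treatment comparison the omission would mostly be a matter of efficiency. The primary question here is different. The coefficient of interest belongs to VDP change, which is observed and not assigned, and nothing in the design balances history or region across its levels. If patients with more past exacerbations also tend to have a different VDP change, part of the slope reflects history. The sponsor could then conclude that the imaging measure predicts exacerbations when it partly restates what the history already showed.

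A link is plausible on the protocol's own account: Section 3.3.1 cites a natural history study relating exacerbations to loss of FEV1. The direction for VDP change is not documented, so confounding could inflate the slope or mask it. If adjustment were left to the sensitivity analyses, masking would go undetected, because those analyses are run only after a positive primary result.

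**Working it through.** **1. The plan's own figure.** The protocol gives no power, precision or effect size for the VDP coefficient. Its one negative binomial figure, 77% in Section 6.1, is for the azithromycin effect. A Wald check with the stated inputs (45 evaluable per arm, one-sided 5%, rate ratio 0.65) gives 42 to 43% if 1.3 is the dispersion k, and 52 to 53% if 1.3 is the size parameter. The 77% is therefore not reproduced. That is a separate matter and does not bear on the covariate question.

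**2. Inputs for the slope.**
- From Sections 4.2 and 6.1: 100 patients, 1:1 allocation, 10% drop-out (90 evaluable), mean of 2 exacerbations, 48 weeks, rate ratio 0.65, over-dispersion 1.3.
- Assumed, with no source in the documents: history strata of equal size (p = 0.5); rate ratio (RR) of 1.5 to 2.0 between 3 or more and 2 prior events; a difference d of 0.3 to 0.5 SD in VDP change between strata; VDP change scaled to SD 1; mean of 2 taken per 52 weeks; 1.3 taken as k; a one-sided 5% test of the slope.

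**3. Shift from omitting history.** Shift = p(1 − p) × d × ln(RR) / Var(VDP change).
- Low: 0.25 × 0.3 × ln 1.5 = 0.030
- High: 0.25 × 0.5 × ln 2 = 0.087

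As rate ratios per SD of VDP change, these are 1.03 and 1.09 from confounding alone.

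**4. Standard error of the slope.** Average mean = 2 × (1 + 0.65)/2 × 48/52 = 1.52. Information per patient = 1.52 / (1 + 1.3 × 1.52) = 0.51. SE = 1/√(n × 0.51) = 0.147 for n = 90 and 0.140 for n = 100.

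**5. Consequence for a true slope of zero, n = 90.**
- Low: 0.030/0.147 = 0.21 SE; 1 − Φ(1.645 − 0.21) = 7.5%
- High: 0.087/0.147 = 0.59 SE; 1 − Φ(1.645 − 0.59) = 14.5%

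With n = 100 the high case is 0.62 SE and 15.3%. The protocol does not say how 1.3 is parameterized. If it is the size parameter (k = 1/1.3 = 0.77), the information is 0.70 per patient, the SE at n = 90 is 0.126, and the two cases become 8% and 17%.

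**6. Simulation check.** 90 patients, k = 1.3, treatment rate ratio 0.65, equal history strata, 600 runs per scenario. With equal strata a difference of d SD is a correlation of d/2, so the range in step 2 corresponds to 0.15 to 0.25. True VDP effect zero:

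| Correlation of VDP change with history | History RR | False positives, history omitted | False positives, history included |
|---|---|---|---|
| 0 | 1.5 | 5.5% | 6.2% |
| 0 | 2.0 | 5.8% | 7.0% |
| 0.2 | 1.5 | 6.8% | 3.8% |
| 0.2 | 2.0 | 14.8% | 7.7% |
| 0.4 | 1.5 | 14.8% | 6.5% |
| 0.4 | 2.0 | 24.0% | 6.2% |

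Monte Carlo error (1.96 × √(q(1 − q)/600), q being the false-positive rate) is about 2 points near 5% and 3 points near 15%. The rows at 0.4 equal a 0.8 SD difference, outside the range in step 2, and are shown only as a stress case. With a true log rate ratio of 0.20 per SD, the model without history returned on average 0.25 to 0.34 at correlations of 0.2 to 0.4; the model with history returned 0.20 to 0.21.

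**The case against.** **The wording sets a floor.** Section 6.4.1 gives a minimum, calls the model initial and points to the SAP. A reader might infer that the primary model adjusts for treatment alone and leaves the strata out, or that the covariates will be chosen after the data are seen. The documents support neither. The SAP may already list the strata, and nothing shows that it was silent or written late. What stands is narrower: the protocol text does not commit to them.

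**History may be a weak covariate here.** Section 3.3.1 reports that exacerbation rates are unstable from year to year and doubts the value of a threshold of two or more events. Cohort A already requires two, so the stratum only separates 2 from 3 or more. The assumed rate ratio of 1.5 to 2.0 has no source. This stands as a limit on the size, not on the direction of the advice, since the sponsor chose history as a stratification factor.

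**The size rests on assumptions.** No document says that VDP change differs by history, and no size was worked out for region. This stands in full: at zero correlation, omitting history does no material harm.

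**A treatment-adjusted association is a legitimate target.** Section 6.1 says that the focus is estimation, and the primary objective is to characterize a relationship. True, but Section 6.1 also sets out to establish whether VDP can predict the exacerbation rate. That claim is hard to interpret without the best known predictor in the model. Both estimates can be reported.

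**Simply adding the strata does not work for all patients.** This is correct and shapes the fix. Cohort B was not randomized and may enter with one exacerbation. The Section 3.1 stratum window is the prior 12 months, whereas Section 4.1.1 accepts any 12-month period within 24 months. An eligible Cohort A patient may therefore have 0 or 1 events in the stratum window.

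**Conclusion.** The point holds as a gap in commitment. Section 6.4.1 names treatment as the only adjustment term, as a minimum, and commits to neither randomization factor, although Section 1.1 ranks exacerbation history first among predictors of the outcome. Because VDP change is not randomized, its slope is open to confounding by history.

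Under the assumptions listed, the shift is 0.03 to 0.09 on the log scale, about 0.2 to 0.6 SE, and a one-sided 5% test would reject falsely in about 7 to 15% of trials. These figures are illustrative. They fall to nothing if VDP change and history are uncorrelated, and confounding in the opposite direction would mask a slope. The change is worth making because it is cheap and bears on the primary claim, not because bias has been shown.

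**What to change.** State in Section 6.4.1 and the synopsis that the reported primary model is fitted in randomized Cohort A as: exacerbation count on VDP change + treatment + region + prior exacerbation history, negative binomial, with log follow-up time as offset. Align the SAP if it differs. The treatment-only model can be shown as supporting.

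Two details need settling at the same time:
- **Cohort B.** Any analysis that includes it should add a cohort term and use the annual exacerbation count recorded at screening (Appendix 1, listed without restriction to a cohort) in place of the 2 versus 3-or-more stratum.
- **Windows.** Reconcile the stratum window in Section 3.1 with the eligibility window in Section 4.1.1, and say how a patient with fewer than two events in the stratum window is classified.

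The cost is protocol and SAP wording and two degrees of freedom; no new data are needed. At correlations of 0.15 to 0.25 between VDP change and history, the SE of the slope grows by a factor of 1/√(1 − 0.15²) = 1.01 to 1/√(1 − 0.25²) = 1.03. The slope is then read as information beyond history, and the text should say so.

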6.4.2 Secondary Efficacy Endpoint

The secondary efficacy endpoint is detailed in Section [2.1.2](#).

Details of the analysis are available in the SAP, including sensitivity analysis around alternative timepoints. Establishing greater sensitivity of ¹²⁹Xe MRI metrics (VDP) will rely on a coefficient of variation test. Establishing correlation of ¹²⁹Xe MRI metrics (VDP) with HRCT metrics will rely on testing the correlation metric.

6.4.3 Exploratory Efficacy Endpoints

The exploratory efficacy endpoints for this study are detailed in Section [2.1.3](#).

Details of the analysis are available in the SAP, including sensitivity analysis around alternative timepoints. Establishing greater sensitivity of ¹²⁹Xe MRI metrics (RDP and VDP), will rely on a coefficient of variation test. Establishing correlation of ¹²⁹Xe MR imaging metrics (RDP and VDP) with other metrics will rely on testing the correlation metric. Prognostic biomarker assessment will be done via linear modeling for primary ¹²⁹Xe MRI endpoints (RDP, VDP, and BDP).

6.5 SAFETY ANALYSES

The safety analysis population will consist of all patients who received at least one dose of study drug during the 48-week open-label treatment period, with patients grouped according to treatment received (AZM + SOC or SOC).

Safety will be assessed through summaries of exposure to study treatment, adverse events, changes in laboratory test results, and changes in vital signs and ECGs (see Section [2.2](#)).

Study treatment exposure (such as treatment duration, total dose received, and number of cycles and dose modifications) will be summarized with descriptive statistics.

All verbatim adverse event terms will be mapped to Medical Dictionary for Regulatory Activities (MedDRA) thesaurus terms, and adverse event severity will be graded according to the WHO toxicity grading scale. All adverse events, serious adverse events, adverse events leading to death, adverse events of special interest, and adverse events leading to study treatment discontinuation that occur on or after the first dose of study treatment (i.e., treatment emergent adverse events) will be summarized by mapped term, appropriate thesaurus level, and severity grade. For events of varying severity, the highest grade will be used in the summaries. Deaths and cause of death will be summarized.

Relevant laboratory, vital sign (pulse rate, respiratory rate, blood pressure, pulse oximetry, and temperature), and ECG data will be displayed by time, with grades identified where appropriate. Additionally, a shift table of selected laboratory tests will be used to summarize the baseline and maximum postbaseline severity grade. Changes in vital signs and ECGs will be summarized.

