2.2 SAFETY OBJECTIVE

The safety objective for this study is to evaluate the safety of ^{129}Xe MRI procedures and of AZM+SOC compared with SOC on the basis of the following endpoints:

- Incidence and severity of adverse events, with severity determined according to the World Health Organization (WHO) toxicity scale
- Change from baseline in targeted vital signs
- Change from baseline in targeted clinical laboratory test results
- Change from baseline in ECG data

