4.3 STUDY INTERVENTIONS AND TREATMENTS RELEVANT TO THE STUDY DESIGN

The IMPs for this study are azithromycin and HP ^{129}Xe . All patients will continue their COPD therapy as recommended in published COPD guidelines (GOLD 2019) or BTS guidelines (NICE 2018). Required COPD inhaler therapies, consisting of LABA and/or LAMA with or without ICS therapy, are considered non-IMPs for this study.

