Appendix 1: Schedule of Activities

	Screening	Treatment Period						End of Tx	Safety Follow-Up ^a	ET ^b	UV
		1	2 ^c	3	4	5	6 ^d				
Visit No.		1	2 ^c	3	4	5	6 ^d	7	8 ^e		
Week (Window, days)		0 -28 to -1	(± 4)	6 (± 4)	12 (± 7)	24 (± 7)	36 (± 7)	48 (± 7)	52 (± 7)		
Concomitant medications		x	x	x	x	x	x	x	x	x	x
AEx			x	x	x	x	x	x	x	x	x
Health care utilizations ^{aa}			x	x	x	x	x	x	x	x	x
Adverse events ^{bb}			x	x	x	x	x	x	x	x	x
Study drug Rx (3-month supply) ^{cc}			x		x	x	x				
Patient diary review ^{dd}				x	x	x	x	x			

6MWT = six-minute walking test; AEx = acute exacerbations; BORG CR10 Scale = Borg Category-Ratio 10 Scale[®]; COPD = chronic obstructive pulmonary disease; CT = computed tomography; DL_{CO} = carbon monoxide diffusing capacity; ET = early termination; FEV₁ = forced expiratory volume; HHIE-S = Hearing Handicap Inventory in the Elderly—Screening Questionnaire; HRCT = high-resolution computed tomography; IRB = Institutional Review Board; KCO = carbon monoxide transfer coefficient; mMRC = Modified Medical Research Council; MRI = magnetic resonance imaging; PRO = patient-reported outcome; Rx = prescription; SGRQ-C = St. George's Respiratory Questionnaire—COPD; SNP = single nucleotide polymorphism; SOA = Schedule of Activities; SOC = standard of care; SpO₂ = oxygen saturation; Tx = treatment; UV = unscheduled visit.

^a Safety follow-up will take place via telephone interview for adverse events, health care utilization, and change in medications.

^b The ET visit applies to patients who discontinue study drug prematurely.

^c All baseline assessments at Visit 2 must be completed prior to the first dose of study drug (azithromycin). Azithromycin will only be dispensed to patients randomized to study drug in Cohort A.

^d Patients in Cohort B will be assessed by telephone call from site staff. Assessments limited to changes in concomitant medications, AEx, health care utilizations, and adverse events occurring between Week 24 and Week 36.

^e Limited to patients in Cohort A only.

^f Written informed consent for participation in the study must be obtained before performing any study-specific tests or evaluations.

^g Demographic data will include age (date of birth), sex, and self-reported race/ethnicity.

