Appendix 1: Schedule of Activities

- ^h Medical history, including clinically significant diseases, surgeries, cancer history (including prior cancer therapies and procedures), reproductive status, medication allergies, smoking history, and use of alcohol and drugs of abuse, will be recorded at screening. In particular, sites should record whether the patient has any history of anaphylaxis, cancer, cardiovascular disease, eosinophilic disease, inflammatory or autoimmune disease or surgeries with metal implants. Any history of smoking should be entered on the Tobacco Use History eCRF.
- ⁱ Vital signs include respiratory rate, pulse rate, systolic and diastolic blood pressure while the patient is in a seated position (resting for at least 5 minutes), temperature, and oxygen saturation.
- ^j Limited physical examination includes head, ears, eyes, nose, throat, cardiovascular, respiratory, and dermatologic examinations.
- ^k ECGs must be performed prior to any scheduled spirometry measurements, vital sign measurements, or blood draws.
- ^l Required hearing *questionnaires* are limited to Cohort A.
- ^m All women of childbearing potential will have a serum pregnancy test at screening. Urine pregnancy tests will be performed at specified subsequent visits. If a urine pregnancy test is positive, it must be confirmed by a serum pregnancy test.
- ⁿ Annual COPD exacerbation rate is determined by a continuous 12-month period within the 24 months prior to screening where a COPD exacerbation is defined by symptomatic worsening of COPD requiring use of systemic corticosteroids and/or antibiotics for at least 3 days, a single depot injectable dose of corticosteroids will be considered.
- ^o PRO questionnaires must be administered prior to the completion of other non-PRO assessments and before the patient receives any disease status information or study drug during that visit.
- ^p mMRC ([Appendix 3](#)) must be administered prior to the completion of other non-PRO assessments and before the patient receives any disease status information or study drug during that visit.
- ^q Includes hemoglobin, hematocrit, platelet count, WBC count, RBC count, and differential count (neutrophils, eosinophils, lymphocytes, monocytes, basophils, other cells).

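### As written, Section 6.5 has an SOC safety group only if about 20 non-randomized GOLD 1 Cohort B patients are in it, which mixes case mix and, to a smaller degree, ascertainment into the azithromycin comparison

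*Combined protocol and SAP*

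**What the plan says.** Section 2.2 sets the safety contrast as that "of AZM+SOC compared with SOC on the basis of the following endpoints". Section 6.5 defines the population: "The safety analysis population will consist of all patients who received at least one dose of study drug during the 48-week open-label treatment period". The same sentence then forms two groups, "with patients grouped according to treatment received (AZM + SOC or SOC". No cohort is mentioned.

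Section 3.1 describes three arms in two cohorts. Cohort A (about 100 patients, GOLD 2–4) is randomized 1:1 to AZM + SOC or SOC. Cohort B (about 20 patients, GOLD 1) is observational, and its single arm is also named SOC.

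The term *study drug* has two possible meanings. Section 4.3 says "The IMPs for this study are azithromycin and HP" ¹²⁹Xe, so every scanned patient receives an investigational product. Appendix 1, footnote c, says that baseline assessments "must be completed prior to the first dose of study drug (azithromycin", which equates study drug with azithromycin.

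The Appendix 1 footnotes give Cohort B a lighter safety schedule:

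- Footnote d, on Visit 6 (Week 36): "Patients in Cohort B will be assessed by telephone call from site staff". The call covers medications, exacerbations, health care use and adverse events only.
- Footnote e, on Visit 8 (Week 52): "Limited to patients in Cohort A only".
- Footnote l, on the HHIE-S: "Required hearing *questionnaires* are limited to Cohort A".

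Section 3.3.2 states the opposite, that Cohort B has the same assessments as Cohort A.

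**The concern.** Grouping by treatment received merges a randomized arm with a non-randomized cohort that has milder disease and a lower entry threshold (at least 1 prior exacerbation rather than at least 2, Section 4.1.1). The AZM + SOC column contains no such patients. The contrast would then no longer be purely the randomized one.

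Two distortions follow. The first is case mix: Section 4.5.13 requires exacerbations to be reported as adverse events, so milder patients can lower the SOC event rate. The second is ascertainment: Cohort B has one laboratory and vital-sign visit fewer, four weeks less follow-up and no hearing questionnaire. Hearing loss and raised liver enzymes are named azithromycin risks (Sections 5.1.2.7 and 5.1.2.8), so the affected summaries are ones that readers will look at.

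**Working it through.** Section 6.5 rests on no stated power or sample size, so there is no figure of the plan to reproduce. The check is by reading and counting.

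**1. Who is in the SOC group.** If study drug is azithromycin alone (footnote c), no SOC patient in either cohort has had a dose, and the SOC group is empty. If it includes ¹²⁹Xe (Section 4.3), all scanned SOC patients qualify, in both cohorts. Neither reading gives an SOC group made up of Cohort A alone.

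**2. Composition.** Cohort A SOC is about 100/2 = 50 and Cohort B about 20. The Cohort B share is 20/(50 + 20) = 28.6%.

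**3. Planned observation, pooled SOC v AZM + SOC.**

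- Follow-up (52 weeks in Cohort A, 48 in Cohort B): (50×52 + 20×48)/70 = 50.9 v 52 weeks, −2.2%.
- Post-baseline laboratory visits (Weeks 6, 12, 24, 36 and 48 as read from Appendix 1; Cohort B lacks Week 36): (50×5 + 20×4)/70 = 4.71 v 5, −5.7%.
- Post-baseline adverse event contacts (the same weeks plus the Week 52 call in Cohort A): (50×6 + 20×5)/70 = 5.71 v 6, −4.8%. The contact lost is Week 52; the Week 36 call still asks about adverse events.

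Fewer draws mainly matter for the shift table of maximum post-baseline grade, since a maximum over four draws cannot exceed the maximum over those four and a fifth.

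**4. Detection of hearing events.** Let *f* be the share of Cohort B events detected, relative to Cohort A. The documents do not give it, so it is an assumption. With no true drug effect, the apparent AZM:SOC risk ratio is 70/(50 + 20*f*):

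- *f* = 1: 70/70 = 1.00
- *f* = 0.8: 70/66 = 1.06
- *f* = 0.5: 70/60 = 1.17
- *f* = 0: 70/50 = 1.40

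The last line is the bound for events found only through the questionnaire; there the SOC risk is understated by 20/70 = 29%.

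**5. Exacerbations counted as adverse events.** Take 2 as the Cohort A SOC rate and a 35% reduction on azithromycin, the planning values in Section 6.1, so the azithromycin rate is 2 × 0.65 = 1.3. The Cohort B rate *r* is assumed. Pooled SOC rate = (50×2 + 20*r*)/70:

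- *r* = 2.0: 2.00, ratio 1.3/2.00 = 0.65
- *r* = 1.5: 1.86, ratio 0.70
- *r* = 1.0: 1.71, ratio 0.76
- *r* = 0.5: 1.57, ratio 0.83

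**6. With SOC limited to Cohort A.** Follow-up is 52 v 52 weeks, laboratory visits 5 v 5, and both arms have the HHIE-S. The ratio in step 4 returns to 1.00 so far as the questionnaire is concerned. Two differences remain. Footnote bb of Appendix 1 directs the hearing query to the azithromycin arm only, whereas Section 4.5.5 directs it to all of Cohort A. Section 5.3.1 ends adverse event reporting 28 days after the last azithromycin dose and gives no end for SOC patients.

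**The case against.** The best defence is that the pooling is an inference. Section 6.5 never names Cohort B, Section 3.1 calls it observational and Section 3.3.1 calls it a separate substudy. The separate SAP is not part of the document reviewed here and may tabulate the cohorts apart. That limit stands. However, Section 6.5, unlike Sections 6.4.1 to 6.4.3, does not defer to the SAP, and its rule applied literally gives either an empty SOC group or a pooled one.

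The second defence is size, and much of it stands. Section 6.5 plans summaries, with no between-group test, in a study described as exploratory. Adverse events are collected at the Cohort B Week 36 call, and Week 52 is only a telephone call in Cohort A. Laboratory data are displayed by time, so a missing Week 36 value there mostly lowers the count at that visit. The HHIE-S is neither a safety endpoint in Section 2.2 nor tabulated in Section 6.5; it can act only through reported hearing events, which Cohort B patients can also volunteer.

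Four stronger readings are tempting and are not supported:

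- A reader might infer that SOC loses 1/5 = 20% of laboratory visits and 4/52 = 7.7% of follow-up. Those figures describe Cohort B alone; in the pooled column they are 5.7% and 2.2%.
- A reader might infer that milder patients in SOC offset the ascertainment effect. They do not: a lower SOC exacerbation rate also makes azithromycin look worse.
- A reader might count the absence of a hearing exclusion in Cohort B as a further cause of low SOC hearing rates. Admitting patients with hearing impairment could as well raise them.
- A reader might infer that Cohort A shares a single ascertainment schedule. Step 6 shows that this is not assured for hearing or for the reporting window.

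**Conclusion.** The point holds in a limited form. Section 6.5 does not define a usable SOC safety group under the azithromycin-only meaning of study drug. Under the meaning that includes xenon, about 29% of SOC is a non-randomized, milder cohort.

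The ascertainment loss is small for ordinary adverse events and laboratory visits (2.2% to 5.7%). It could be larger for questionnaire-prompted hearing events: an apparent ratio between 1.00 and 1.40 with no true effect, depending on an assumed detection share. The case-mix effect on exacerbation events could move a true 0.65 to as much as 0.83. That rests on assumed Cohort B rates of 0.5 to 2.0 and on counting events, which Section 6.5 does not specify.

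The documents do not support a general statement that SOC harm is substantially under-recorded. They do support a change to the grouping rule, which should be made because it is cheap and restores the randomized comparison.

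**What to change.** In Section 6.5:

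- Base the AZM + SOC v SOC safety comparison on randomized Cohort A (about 50 v 50), and show Cohort B in its own descriptive column.
- Combine all patients only for events related to the xenon procedure.
- Define *study drug* for the safety population so that the SOC arm is included.

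Elsewhere:

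- State an adverse event cut-off for SOC patients, since Section 5.3.1 ties it to the last azithromycin dose.
- Reconcile Section 3.3.2 with footnotes d, e and l of Appendix 1.
- Reconcile Section 4.5.5 with footnote bb on who is asked about hearing. Restricting the comparison to Cohort A does not remove that difference.

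The cost is a few sentences and one table column, with no new data. The SOC comparator falls from about 70 to about 50 patients. If the SAP already separates the cohorts, Section 6.5 needs only to say so, along with the definitions and reconciliations above.
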